### **Objectives:**

#### *Primary endpoint:*

1) to compare the **efficacy** of HnB and EC, in terms of quit rates at week 12, by self-reporting abstinence from classic cigarette [validated by an Exhaled breath Carbon monoxide (eCO) measurement  $\leq 10\text{ppm}$ ]

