### **Efficacy assessment:**

The **efficacy** of HnB and EC, in terms of quit rates, will be assessed by self-reporting abstinence from classic cigarette [validated by an Exhaled breath Carbon monoxide (eCO) measurement  $\leq 10$ ppm]. Abstinence from smoking, defined as complete self-reported abstinence from tobacco smoking - not even a puff (together with an eCO concentration of  $\leq 10$ ppm) since the previous study visit, will be calculated at each study visit (“quitters”), including at week 24. Primary endpoint is, however, fixed at week 12.

1. Caponnetto P, Campagna D, Cibella F, et al. (2013a) Efficiency and Safety of an eElectronic cigarette (ECLAT) as Tobacco Cigarettes Substitute: A Prospective 12-Month Randomized Control Design Study. PLoS One, 8(6):e66317.

---

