### 2.2 Study Objectives

The primary objective of this study is to compare the efficacy of HnB and EC, in terms of quit rates at week 12, by self-reporting abstinence from classic cigarette [validated by an Exhaled breath Carbon monoxide (eCO) measurement  $\leq 10$ ppm].

The secondary objectives are:

- 1) to compare the smoking reduction derived from the use of HnB and EC, intended as a 50% reduction in the number of conventional cigarette/day at week 12, defined through self-reporting;
- 2) to compare the adoption rate, and adherence to product use [by collecting (empty) refill bottles and used heatsticks on a daily basis, verified by a study diary filled daily by the subject];
- 3) to compare the acceptability of HnB and of EC, through the assessment of product satisfaction, risk perception, effects on craving and nicotine withdrawal, product preferences, subjective and sensorial effects by:
  - a) Modified Cigarette Evaluation Questionnaire (mCEQ) adapted for EC and HnB users;
  - b) three of 8 items of "Smoking Cue Appeal" adapted for EC and HnBusers;
  - c) "Intent to use questionnaire" (ITUQ) – items 4-6;
  - d) PRI-P CC Perceived Health Risk scale (for classic cigarette)
  - e) PRI-P RRP Perceived Health Risk scale (for reduced risk products)
  - f) percentage of choice of a particular subtype of heatstick (HnB) or e-liquid.
- 4) to compare the tolerability of HnB and EC, in terms of: self-reported adverse and serious adverse events by study participants, vital signs (BP, HR and body weight) measurements.
- 5) to compare the tobacco harm reduction between HnB and EC, in terms of:
  - a) changes in Biomarkers of Biological Effects (BoBE) such as: eCO in the exhaled breath (i.e. eCO), step test values;

	
e-CIG VS. IQOS Statistical Analysis Plan Version 2.0
	Doc code: BIOSTAT.SAP.02
		Pag. 8 of 115

b) measurement of 14 selected Biomarkers of Exposure (BoE) in spot urine samples of study participants:

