## 7.1 Analysis of primary endpoint

The primary endpoint aims to compare the efficacy of HnB and EC in terms of quit rates at week 12 by means a non-inferiority threshold of 15%.

A "Continuous Quitter" is defined as a subject who has a number of conventional cigarette/day equal to zero from Visit 4 to Visit 6. The Farrington-Manning Score Test for Proportion Difference will be used for comparing the quit rates of the two groups. The SAS® PROC FREQ with the METHOD=FM option will be used. The quit rates of the two groups, along with the relevant 95% Confidence Intervals, will be summarized in Table E.1 (Appendix 2).

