### **7.2.1 Smoking reduction derived from the use of HnB and EC**

The smoking reduction derived from the use of HnB and EC, will be computed at each visit. The analysis will be presented considering both the definition of “Reducer” included in the study protocol and the so called “Russell Standard” (clinical) for outcome assessment in clinical trials of smoking cessation treatments.

As for the protocol definition, a subject will be classified as “Reducer” if at least a 50% reduction in the number of conventional cigarette/day at each visit will be observed. The results will be summarized as frequency table. The comparison between the two groups will be performed at each visit with the chi-square test. The results will be included in Table E.2a (Appendix 2).

As for the Russell Standard analysis, due to the fact that the study endpoint was a 12 weeks, a small deviation was adopted. In fact, the timepoint considered in the Russell Standard is 52 week. In our case, the 12 week and the 24 week (i.e. the Follow-up observation) will be considered for the analysis. The results will be included in Table E.2b (Appendix 2).

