## EFFICACY ENDPOINTS

	e-CIG VS. IQOS Statistical Analysis Plan Version 2.0	Doc code: BIOSTAT.SAP.02
		Pag. 42 of 115

Sponsor: Center for Tobacco Research, Cessation and Prevention, [name]  
Protocol: Progetto e-cig vs IQOS

Table E.1a Summary of the Primary End-point. Quit Rate at all visits  
Population: <Per-Protocol/Intention-To-Treat>

			Group HnB N=XXXX	Group EC N=XXXX
Quit rate	Visit 1	N(%)	XXX (XX.X%)	XXX (XX.X%)
	Visit 2	N(%)	XXX (XX.X%)	XXX (XX.X%)
	...	N(%)	XXX (XX.X%)	XXX (XX.X%)
	Visit n	N(%)	XXX (XX.X%)	XXX (XX.X%)

<File: [..]\Work\_In\_Progress\[..]\Statistica\Programmi\xxxxx.sas>

<Source: [..]\Work\_In\_Progress\[..]\Gestione Dati\Dati SAS\xxxxx.sas7bdat>      Generated on XXXXXXXXXX XX:XX

As for the PP population, a "Continuous Quitter" is defined as the subject who did not smoke conventional cigarettes from visit 4 to visit 6

The p-value was derived from the XXXX test

For further information see Listing X.X

Sponsor: Center for Tobacco Research, Cessation and Prevention, [name]  
Protocol: Progetto e-cig vs IQOS

Table E.1b Summary of the Primary End-point. Quit Rate at final visit comparison  
Population: <Per-Protocol/Intention-To-Treat>

		Group HnB N=XXXX	Group EC N=XXXX
Quit Rate	Rate 95%CI	XX.X% [XX.XX,XXX.X]	XX.X% [XX.XX,XXX.X]

H0: P1-P2 ≤ -Margin  
H1: P1-P2 > -Margin

Margin=X.XXX

Score (Farrington-Manning)

Proportion Difference	ASE (F-M)	Z	Pr>Z
X.XXXX	X.XXXX	X.XXXX	X.XXXX

Noninferiority Limit	95% Confedent Limits	
X.XXXX	X.XXXX	X.XXXX

<File: [..]\Work\_In\_Progress\[..]\Statistica\Programmi\xxxxx.sas>

<Source: [..]\Work\_In\_Progress\[..]\Gestione Dati\Dati SAS\xxxxx.sas7bdat>      Generated on XXXXXXXXXX XX:XX

As for the PP population, a "Continuous Quitter" is defined as the subject who did not smoke conventional cigarettes from visit 4 to visit 6  
For further information see Listing X.X

	e-CIG VS. IQOS Statistical Analysis Plan Version 2.0	Doc code: BIOSTAT.SAP.02
		Pag. 44 of 115

Sponsor: Center for Tobacco Research, Cessation and Prevention, [name]  
Protocol: Progetto e-cig vs IQOS

Table E.2a Summary of Smoking Reduction derived from the use of HnB and EC at week 12  
Population: <Per-Protocol/Intention-To-Treat>

		Group HnB	Group EC	p-value
		N=XXXX	N=XXXX	
Smoking Reduction	Rate 95%CI	XX.X% [XX.XX,XXX.X]	XX.X% [XX.XX,XXX.X]	X.XXXX

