<File: [..]\Work\_In\_Progress\[..]\Statistica\Programmi\xxxxx.sas>  
<Source: [..]\Work\_In\_Progress\[..]\Gestione Dati\Dati SAS\xxxxx.sas7bdat>      Generated on XXXXXXXXXX XX:XX  
Smoking reduction is intended as a least a 50% reduction in the number of conventional cigarette/day at week 12.  
The p-value was derived from the XXXX test  
For further information see Listing X.X

Sponsor: Center for Tobacco Research, Cessation and Prevention, [name]  
Protocol: Progetto e-cig vs IQOS

Table E.2b Summary of Smoking Reduction derived from the use of HnB and EC according to the Russell Standard Population: <Per-Protocol/Intention-To-Treat>

Quit timepoint		Group HnB	Group EC	p-value
		N=XXX	N=XXX	
Self-reported 4 week	Rate	XX.X%	XX.X%	X.XXXX
	95%CIIs	[XX.XX,XXX.X]	[XX.XX,XXX.X]	
eCO checked* 4 weeks	Rate	XX.X%	XX.X%	X.XXXX
	95%CIIs	[XX.XX,XXX.X]	[XX.XX,XXX.X]	
eCO checked* 12 weeks	Rate	XX.X%	XX.X%	X.XXXX
	95%CIIs	[XX.XX,XXX.X]	[XX.XX,XXX.X]	
eCO checked* 24 weeks	Rate	XX.X%	XX.X%	X.XXXX
	95%CIIs	[XX.XX,XXX.X]	[XX.XX,XXX.X]	
Lost to FU 24 weeks	Rate	XX.X%	XX.X%	X.XXXX
	95%CIIs	[XX.XX,XXX.X]	[XX.XX,XXX.X]	

<File: [..]\Work\_In\_Progress\[..]\Statistica\Programmi\xxxxx.sas>  
<Source: [..]\Work\_In\_Progress\[..]\Gestione Dati\Dati SAS\xxxxx.sas7bdat>      Generated on XXXXXXXXXX XX:XX

\* expired-air 'CO-verified (eCO) 4-week quitter' is the subject that was found to be less than 10ppm in the past 2 weeks  
The p-value was derived from the XXXX test  
For further information see Listing X.X

	e-CIG VS. IQOS Statistical Analysis Plan Version 2.0	Doc code: BIOSTAT.SAP.02
		Pag. 46 of 115

Sponsor: Center for Tobacco Research, Cessation and Prevention, [name]  
Protocol: Progetto e-cig vs IQOS

Table E.3 Summary of Adoption Rate and Adherence to product use at week 12  
Population: <Per-Protocol/Intention-To-Treat>

		Group HnB	Group EC	p-value
		N=XXXX	N=XXXX	
Adoption Rate	Rate 95%CIs	XX.X% [XX.XX, XXX.X]	XX.X% [XX.XX, XXX.X]	X.XXXX

<File: [..]\Work\_In\_Progress\[..]\Statistica\Programmi\xxxxx.sas>  
<Source: [..]\Work\_In\_Progress\[..]\Gestione Dati\Dati SAS\xxxxx.sas7bdat>      Generated on XXXXXXXXXX XX:XX  
A subject is defined as "Compliant" if he/she used at least a 90% of the product  
The p-value was derived from the XXXX test  
For further information see Listing X.X

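### The Table E.2b footnote defines a CO-verified quitter by a low eCO reading and omits self-reported abstinence, so literal programming would count low-CO smokers as quitters

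*SAP*

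**What the plan says.** - **Protocol, Primary endpoint.** HnB and EC are compared "in terms of quit rates at week 12, by self-reporting abstinence from classic cigarette [validated by an Exhaled breath Carbon monoxide (eCO) measurement" ≤10 ppm.
- **Protocol, Efficacy assessment.** Abstinence is "defined as complete self-reported abstinence from tobacco smoking - not even a puff (together with an eCO concentration of" ≤10 ppm). It covers the time since the previous study visit and is assessed at every visit, including week 24.
- **SAP 2.2.** The primary objective again joins the two conditions: "self-reporting abstinence from classic cigarette [validated by an Exhaled breath Carbon monoxide (eCO) measurement" ≤10 ppm.
- **SAP 7.2.1.** A Russell Standard analysis is added. The SAP says that "a small deviation was adopted" and explains it purely as timing: 12 and 24 weeks in place of 52.
- **SAP Appendix 2, Table E.2b.** One self-reported row, at 4 weeks, is followed by three starred eCO-checked rows at 4, 12 and 24 weeks, each with a between-arm p-value. According to the footnote, the CO-verified 4-week quitter "is the subject that was found to be less than 10ppm in the past 2 weeks".
- **Protocol, Visit schedule description (remark on product use).** Participants may smoke their own cigarettes as they wish alongside the allocated product.

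**The concern.** The footnote is the rule a programmer would code, and it contains one condition where the protocol has two. eCO is meant to confirm a claim of abstinence. On its own it is also one of the trial's harm-reduction measures (Protocol, Tobacco Harm Reduction assessment), and it can fall in someone who has cut down but still smokes. Dual use is allowed and reducers are a separate outcome, so a low reading does not identify a quitter in this population.

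Verification should only lower a self-reported rate. Under the footnote's literal rule, the eCO-checked rate could exceed the self-reported one. In this table that would be visible only at week 4, because weeks 12 and 24 have no self-reported row.

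The rows also attract attention. SAP 7.1 and the footnotes to Tables E.1a and E.1b define the Continuous Quitter by zero cigarettes from Visit 4 to Visit 6 and do not mention eCO. A reader who wants CO-validated quitting will turn to Table E.2b.

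**Working it through.** **1. The plan's own figure.** The only design figure on quit rates is 104 per group (Protocol, Sample size calculation; SAP 3). The inputs are a rate of 0.25 in both arms, margin 0.15, one-sided alpha 0.05 and power 0.80. The Farrington-Manning restricted estimates under the null are 0.189 and 0.339, giving n = 103.48, rounded up to 104. The figure is reproduced, and nothing in this point changes it.

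**2. The definitions side by side.**

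| Source | Self-reported abstinence | eCO | Timing of eCO |
|---|---|---|---|
| Protocol, Efficacy assessment | yes, since previous visit | ≤10 ppm | at each study visit |
| SAP 2.2 | yes | ≤10 ppm | week 12 |
| SAP 7.1, Continuous Quitter | yes, zero cigarettes V4 to V6 | not stated | – |
| Table E.2b footnote | not stated | <10 ppm | past 2 weeks |

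The footnote differs from the protocol in three ways: no abstinence condition, a strict inequality, and a look-back in place of a same-visit reading. It also describes a 4-week quitter while being starred on the 12- and 24-week rows.

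**3. The look-back.** V3 is at day 14 ± 3 and V4 at day 28 ± 3 (Protocol, Visit schedule).
- The nominal gap is 28 − 14 = 14 days, and the range is 14 − 6 = 8 to 14 + 6 = 20 days. A V3 reading therefore falls within two weeks of V4 for some subjects and not for others, depending on scheduling.
- At week 12 the nominal gap from V5 is 28 days. It reaches 28 − 14 = 14 only if both visits sit at opposite edges of their ± 7-day windows.
- At week 24 the smallest gap from V6 is 84 − 14 = 70 days.
- In practice the problem is confined to week 4.

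**4. Size under literal programming.** Let q be the true quit rate and s the share of non-abstinent subjects with a low reading. The literal rate is q + s(1 − q). The documents give q = 20–25% but no value for s, so s = 5–20% is an assumption.

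| q | s | Literal rate | Share of counted quitters who smoke |
|---|---|---|---|
| 25% | 5% | 0.25 + 0.05 × 0.75 = 28.75% | 0.0375 / 0.2875 = 13% |
| 25% | 10% | 0.25 + 0.10 × 0.75 = 32.5% | 0.075 / 0.325 = 23% |
| 25% | 20% | 0.25 + 0.20 × 0.75 = 40% | 0.15 / 0.40 = 37.5% |
| 20% | 5% | 0.20 + 0.05 × 0.80 = 24% | 0.04 / 0.24 = 17% |
| 20% | 20% | 0.20 + 0.20 × 0.80 = 36% | 0.16 / 0.36 = 44% |

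**5. Effect on the comparison.** With the same s in both arms, a true difference is multiplied by (1 − s). A difference of −15 points becomes −15 × 0.95 = −14.25 at s = 5% and −15 × 0.80 = −12 at s = 20%. With equal true rates of 25% and a 10-point gap in s between arms, a false difference of 0.75 × 0.10 = 7.5 points appears.

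**6. With both conditions required**, a smoker who reports smoking cannot be counted. For these subjects s is then zero, and the excess disappears.

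**The case against.** The strongest reply is that the footnote was never meant to stand alone. Its subject is a CO-verified quitter, the column is headed as a quit time point, and the eCO-checked rows follow a self-reported row. A programmer could reasonably take the self-reported quitters and then check their eCO. Under that reading the inflation is zero. This stands: a reader might infer that dual users and reducers will be counted, but the documents show only that they would be if the rule were coded as written, and then only those with a low reading. The reading does not settle the matter, because the length of abstinence is still not given. It could be since the previous visit, zero cigarettes from V4 to V6, or an undefined four-week self-report.

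A reader might also infer that nothing else in the SAP requires both conditions. SAP 2.2 does require them. What can be said is that the footnote neither repeats SAP 2.2 nor refers to it, and that Table E.2b holds the only rows labelled CO-checked.

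Nor can the footnote be called an undeclared departure from the Russell Standard, since the documents do not reproduce that standard. The conflict shown is with the protocol and with SAP 2.2.

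Finally, no direction of bias between the arms is shown, and the values of s are illustrative.

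**Conclusion.** The point holds as a conflict between a stated output rule and the endpoint definition. The E.2b footnote requires only a low eCO; the protocol and SAP 2.2 require abstinence as well, and SAP 7.2.1 does not declare the change. Coded literally, and assuming that 5–20% of non-abstinent subjects read low, a 25% rate would be shown as about 29–40%. The true share is not in the documents, so the real effect is unknown, and it is nil if eCO is checked only among self-reported quitters. At week 4 the look-back adds a second weakness when V3 and V4 are 14 days or less apart.

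It would be wrong to conclude that the primary result is at risk. Table E.2b is secondary and does not feed the non-inferiority test in Table E.1b or the sample size. The footnote should be corrected before the table is programmed, because it carries between-arm p-values under a label that promises verification.

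**What to change.** In the Table E.2b footnote and in SAP 7.2.1, define the eCO-checked quitter at weeks 4, 12 and 24 as a subject who meets both conditions:

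- self-reported abstinence from conventional cigarettes since the previous study visit (the protocol's definition), or over another stated period if the Russell Standard analysis needs one; and
- eCO ≤10 ppm measured at that same visit.

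State that a subject with either item missing is not a quitter. The existing failure rules (SAP 5; Data Review Meeting minute 2.4) cover drop-outs and losses to follow-up, but do not address someone who attends without a usable eCO reading.

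The cost is one footnote, one sentence in 7.2.1 and one programming condition. Cigarettes per day and eCO are already recorded by visit (Listing D.4b). The downside is that the eCO-checked rates may be lower. Retitling the table as quit rates instead of smoking reduction would help readers, but is optional and editorial.

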**Acceptability assessment:**

Product satisfaction, effects on craving and nicotine withdrawal, product preferences, risk perception, subjective and sensorial effects to compare the acceptability of HnB and of EC, will be evaluated at wk 4, wk 8, wk 12 (+ follow-up at wk 24), by using:

- a) Modified Cigarette Evaluation Questionnaire (mCEQ) adapted for EC and HnB users;
- b) three of 8 items of “Smoking Cue Appeal” adapted for EC and HnBusers;
- c) “Intent to use questionnaire” (ITUQ) – items 4-6;
- d) PRI-P CC Perceived Health Risk scale (for classic cigarette)
- e) PRI-P RRP Perceived Health Risk scale (for reduced risk products)
- f) percentage of choice of a particular subtype of heatstick (HnB) or e-liquid.

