### 7.2.4 Smoking Cue Appeal Questionnaire

The Smoking Cue Appeal Questionnaire will be presented as frequency table of the scores for each question included in the questionnaire. Each table will compare, for each visit in which the questionnaire was administered, the Hnb group and the EC group frequency of answers (Table E.4b1).

The t-test will be carried out on the differences at final visit to baseline. In case the normality assumption is not verified, the corresponding non parametric test will be adopted (Table E.4b2). These data will also be listed (Appendix 3: Listing E.3).

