Sponsor: Center for Tobacco Research, Cessation and Prevention, [name]  
Protocol: Progetto e-cig vs IQOS

Table E.4a2 mCE Questionnaire (scores). Inferential analysis on the mean changes at final visit from baseline  
Population: <Per-Protocol/Intention-To-Treat>

		Group HnB N=XXXX	Group EC N=XXXX	p-value
Satisfaction	Mean	XX.X	XX.X	X.XXXX
Psychological Reward	Mean	XX.X	XX.X	X.XXXX
Aversion	Mean	XX.X	XX.X	X.XXXX
Enjoyment of Sensation	Mean	XX.X	XX.X	X.XXXX
Craving Reduction	Mean	XX.X	XX.X	X.XXXX
TOTAL	Mean	XX.X	XX.X	X.XXXX

Sponsor: Center for Tobacco Research, Cessation and Prevention, [name]  
Protocol: Progetto e-cig vs IQOS

Table E.4b1 Summary of Smoking Cue Appeal Questionnaire by visit. <Question 1 of 8>  
Population: <Per-Protocol/Intention-To-Treat>

<Question>

Visit	Score	Group HnB	Group EC
Visit 4	1	XX (XX.X%)	XX (XX.X)
	2	XX (XX.X%)	XX (XX.X)
	3	XX (XX.X%)	XX (XX.X)
	4	XX (XX.X%)	XX (XX.X)
	5	XX (XX.X%)	XX (XX.X)
	6	XX (XX.X%)	XX (XX.X)
	7	XX (XX.X%)	XX (XX.X)
Visit 5	1	XX (XX.X%)	XX (XX.X)
	2	XX (XX.X%)	XX (XX.X)
	3	XX (XX.X%)	XX (XX.X)
	4	XX (XX.X%)	XX (XX.X)
	5	XX (XX.X%)	XX (XX.X)
	6	XX (XX.X%)	XX (XX.X)
	7	XX (XX.X%)	XX (XX.X)
Visit 6	1	XX (XX.X%)	XX (XX.X)
	2	XX (XX.X%)	XX (XX.X)
	3	XX (XX.X%)	XX (XX.X)
	4	XX (XX.X%)	XX (XX.X)
	5	XX (XX.X%)	XX (XX.X)
	6	XX (XX.X%)	XX (XX.X)
	7	XX (XX.X%)	XX (XX.X)
Visit 7	1	XX (XX.X%)	XX (XX.X)
	2	XX (XX.X%)	XX (XX.X)
	3	XX (XX.X%)	XX (XX.X)
	4	XX (XX.X%)	XX (XX.X)
	5	XX (XX.X%)	XX (XX.X)
	6	XX (XX.X%)	XX (XX.X)
	7	XX (XX.X%)	XX (XX.X)

<File: [..]\Work\_In\_Progress\[..]\Statistica\Programmi\xxxxx.sas>

<Source: [..]\Work\_In\_Progress\[..]\Gestione Dati\Dati SAS\xxxxx.satd7sas> Generated on XXXXXXXX XX:XX

Legend: 1. Estremamente sgradevole ; 2. Molto sgradevole ; 3. Sgradevole ; 4. Né piacevole, né sgradevole ; 5. Piacevole  
6. Molto piacevole ; 7. Estremamente piacevole

For further information see Listing X.X

	e-CIG VS. IQOS Statistical Analysis Plan Version 2.0	Doc code: BIOSTAT.SAP.02
		Pag. 50 of 115

Sponsor: Center for Tobacco Research, Cessation and Prevention, [name]  
Protocol: Progetto e-cig vs IQOS

Table E.4b2 Smoking Cue Appeal Questionnaire. Inferential analysis on the mean changes at final visit from baseline  
Population: <Per-Protocol/Intention-To-Treat>

		Group HnB N=XXXX	Group EC N=XXXX	p-value
Question 1	Mean	XX.X	XX.X	X.XXXX
Question 2	Mean	XX.X	XX.X	X.XXXX

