...	Mean	XX.X	XX.X	X.XXXX
Question 8	Mean	XX.X	XX.X	X.XXXX
TOTAL	Mean	XX.X	XX.X	X.XXXX

<File: [..]\Work\_In\_Progress\[..]\Statistica\Programmi\xxxxx.sas>  
<Source: [..]\Work\_In\_Progress\[..]\Gestione Dati\Dati SAS\xxxxx.sas7bdat>      Generated on XXXXXXXXXX XX:XX  
For the inferential analysis, the scores were considered as numbers.  
The p-value was derived from the XXXX test  
For further information see Listing X.X

Sponsor: Center for Tobacco Research, Cessation and Prevention, [name]  
Protocol: Progetto e-cig vs IQOS

Table E.4c1 Summary of the ITU Questionnaire by visit. <Question 4 (of questions 4-5-6)>  
Population: <Per-Protocol/Intention-To-Treat>

<Question>

Visit	Score	Group HnB	Group EC
Visit 4	1	XX (XX.X%)	XX (XX.X)
	2	XX (XX.X%)	XX (XX.X)
	3	XX (XX.X%)	XX (XX.X)
	4	XX (XX.X%)	XX (XX.X)
	5	XX (XX.X%)	XX (XX.X)
	6	XX (XX.X%)	XX (XX.X)
	7	XX (XX.X%)	XX (XX.X)
Visit 5	1	XX (XX.X%)	XX (XX.X)
	2	XX (XX.X%)	XX (XX.X)
	3	XX (XX.X%)	XX (XX.X)
	4	XX (XX.X%)	XX (XX.X)
	5	XX (XX.X%)	XX (XX.X)
	6	XX (XX.X%)	XX (XX.X)
	7	XX (XX.X%)	XX (XX.X)
Visit 6	1	XX (XX.X%)	XX (XX.X)
	2	XX (XX.X%)	XX (XX.X)
	3	XX (XX.X%)	XX (XX.X)
	4	XX (XX.X%)	XX (XX.X)
	5	XX (XX.X%)	XX (XX.X)
	6	XX (XX.X%)	XX (XX.X)
	7	XX (XX.X%)	XX (XX.X)
Visit 7	1	XX (XX.X%)	XX (XX.X)
	2	XX (XX.X%)	XX (XX.X)
	3	XX (XX.X%)	XX (XX.X)
	4	XX (XX.X%)	XX (XX.X)
	5	XX (XX.X%)	XX (XX.X)
	6	XX (XX.X%)	XX (XX.X)
	7	XX (XX.X%)	XX (XX.X)

<File: [..]\Work\_In\_Progress\[..]\Statistica\Programmi\xxxxx.sas>

<Source: [..]\Work\_In\_Progress\[..]\Gestione Dati\Dati SAS\xxxxx.satd7sas> Generated on XXXXXXXX XX:XX

Legend: 1. Assolutamente falso ; 2. Falso ; 3. Piuttosto falso ; 4. Piuttosto vero ; 5. Vero ; 6. Molto vero ; 7. Verissimo

For further information see Listing X.X

Sponsor: Center for Tobacco Research, Cessation and Prevention, [name]  
Protocol: Progetto e-cig vs IQOS

Table E.4c2 ITU Questionnaire. Inferential analysis on the mean changes at final visit from baseline  
Population: <Per-Protocol/Intention-To-Treat>

		Group HnB N=XXXX	Group EC N=XXXX	p-value
Question 4	Mean	XX.X	XX.X	X.XXXX
Question 5	Mean	XX.X	XX.X	X.XXXX
Question 6	Mean	XX.X	XX.X	X.XXXX
TOTAL	Mean	XX.X	XX.X	X.XXXX

Sponsor: Center for Tobacco Research, Cessation and Prevention, [name]  
Protocol: Progetto e-cig vs IQOS

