## **APPENDIX 4 Flow Chart**

	V0 screening	V1 baseline	V2	V3	V4	V5	V6	V7 follow-up
Assessment		≤ 7 days after V0	1 week after visit 1 +/-3 days	2 weeks after visit 1 +/-3 days	4 weeks after visit 1 +/-3 days	8 weeks after visit 1 +/-7 days	12 weeks after visit 1 +/-7 days	24 weeks after visit 1 +/-7 days
Medical/smoking/vaping/new generation product use history	X							X
Instructions for urine collection and storage; delivery of containers	X			X				
Eligibility criteria verification and confirmation	X							
Informed consent	X							
Vital Signs (BP, HR)		X	X	X	X	X	X	X
Weight and Height		X					X	X
Urine sample pick up		X			X			
Randomization		X						
Training for the allocated device (from 30min to 2 hours)		X						
Device delivery (included 1 week supply heatsticks for iQOS or eliquid for JustFog)		X						
Providing 1 week supply of heatsticks for iQOS or eliquid for JustFog			X					
Providing 2 weeks supply of heatsticks for iQOS or eliquid for JustFog				X				

Providing 4 weeks supply of heatsticks for iQOS or eliquid for JustFog					X	X		
Smoking consumption/abstinence/reduction recording through subject selfreporting		X	X	X	X	X	X	X
Device and supply accountability (collection of empty e-liquid refill bottles and used heathsticks; eventual substitution of malfunctioning devices)			X	X	X	X	X	X
mCEQ					X	X	X	X
Smoking Cue Appeal (8 items)					X	X	X	X
ITUQ – items 4-6					X	X	X	X
Risk perception (PRI-P CC e PRIP RRP)					X	X	X	X
EQ-5D		X			X	X	X	X
eCO		X	X	X	X	X	X	X
Step test		X			X		X	X
Safety and product reliability onitoring reporting		X	X	X	X	X	X	X

e-CIG VS. IQOS  
Statistical Analysis Plan  
Version 1.1

Doc code:  
BIOSTAT.SAP.02

Pag. 95 of 115

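### The Smoking Cue Appeal endpoint is worded as three items, but the SAP tables test all eight plus a TOTAL and never isolate the three

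*SAP*

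**What the plan says.** The protocol (Secondary endpoints, item 4b, and again under Acceptability assessment) and SAP 2.2 (objective 3b) define the measure in the same terms: "three of 8 items of 'Smoking Cue Appeal' adapted for EC and HnBusers".

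The visit schedules give a different count. The protocol visit schedule and the SAP Appendix 4 flow chart both list eight items, the latter as "Smoking Cue Appeal (8 items)", at Visits 4, 5, 6 and 7. Neither marks an administration at Visit 1.

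The SAP analysis follows the schedules. Section 7.2.4 says that the questionnaire "will be presented as frequency table of the scores for each question included in the questionnaire", followed by a t-test (or its non-parametric counterpart) on the difference between final visit and baseline. In Appendix 2 the frequency shell is "Table E.4b1 Summary of Smoking Cue Appeal Questionnaire by visit. <Question 1 of 8>". Table E.4b2 has a mean per arm and a p-value for Questions 1 to 8 and for a further row, TOTAL. Its only scoring note is "For the inferential analysis, the scores were considered as numbers". Listing E.3 in Appendix 3 has columns Q1 to Q8.

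**The concern.** An endpoint stated as three items should be recognisable in the analysis as three items. Here it is not. Nine p-values are planned, none is marked as the endpoint, and the three items are not named in either document. Whoever writes the report would have to choose, after the results are visible and in an open-label trial, which rows represent product appeal. The TOTAL row is the natural one to quote because it is a single number, yet it includes items that the stated endpoint does not.

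The Intent to Use Questionnaire shows that this is not just how the tables are laid out. That endpoint is items 4 to 6, and its shell is restricted to match: "Table E.4c1 Summary of the ITU Questionnaire by visit. <Question 4 (of questions 4-5-6)>". The TOTAL in Table E.4c2 follows only those three rows. The restriction was carried through for one questionnaire and not for the other, and SAP 7.2.4 does not declare the difference as a change.

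**Working it through.** There is no figure in the plan to reproduce. The check compares item counts and works out what follows from them.

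**Inputs**

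| Place | Items |
|---|---|
| Protocol, Secondary endpoints 4b | 3 of 8 |
| Protocol, Acceptability assessment | 3 of 8 |
| SAP 2.2, objective 3b | 3 of 8 |
| Protocol visit schedule | 8, at V4 to V7 |
| SAP Appendix 4 flow chart | 8, at V4 to V7 |
| SAP 7.2.4 | every question, no restriction |
| SAP Table E.4b1 | 8 |
| SAP Table E.4b2 | 8, plus TOTAL |
| SAP Listing E.3 | 8 |

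**Number of tests.** Table E.4b2: 8 items + 1 TOTAL = 9. The stated endpoint would need 3, or 4 with a three-item total. At 0.05 each, the chance of at least one false positive under independence is 1 − 0.95^k:
- k = 9: 0.37
- k = 4: 0.19
- k = 3: 0.14

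The rows are correlated, so these values only illustrate the scale.

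**Composition of TOTAL.** No scoring rule is given. If TOTAL is an equally weighted sum (an assumption), 8 − 3 = 5 of its 8 items, or 5/8 = 62.5%, lie outside the stated endpoint. On the 1 to 7 scale its range is 8 to 56, against 3 to 21 for a three-item sum.

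**How far the two sums could differ.** Assume equal item variances and a common inter-item correlation r. In units of the item variance, var(3-item sum) = 3 + 6r, var(8-item sum) = 8 + 56r, and their covariance = 3 + 6r + 15r = 3 + 21r. The correlation between the sums is (3 + 21r)/√[(3 + 6r)(8 + 56r)]:
- r = 0: 0.61
- r = 0.3: 0.85
- r = 0.5: 0.92
- r = 0.7: 0.96

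The documents give no value for r. If the items move together, the two sums largely agree. If they do not, TOTAL measures something else.

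**The tested contrast.** Section 7.2.4 and Table E.4b2 test change from baseline. Both schedules start the questionnaire at Visit 4, and Table E.4b1 also begins at Visit 4. No baseline score exists to subtract, for three items or for eight.

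**The case against.** The strongest reply is that the SAP has not departed from a settled endpoint. The protocol's own visit schedule lists eight items and the SAP shells match it. This stands: the conflict is already inside the protocol, and collecting eight items is not a fault of the SAP. It does not explain why the analysis never identifies the three.

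The endpoint phrase can also be read as eight items given, of which three are adapted to the study products. The adapted questionnaire is not in the documents, so this cannot be settled here. Under that reading TOTAL would mix adapted with unadapted items, and the three would still be unnamed.

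A reader might infer that the reported endpoint is an eight-item sum in which a product difference is swamped. For instance, a 1-point difference on only the three items becomes 3/8 = 0.375 on an eight-item average. The documents do not support that. Table E.4b2 gives every question its own row and p-value, so a difference on any item stays visible. SAP 7.2.4 does not mention a TOTAL, and nothing makes that row the endpoint. The 0.375 also rests on an assumed effect pattern and an assumed scoring rule. Dilution can touch the TOTAL row only.

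Finally, this is one of six acceptability measures within one secondary endpoint, in an analysis that SAP section 5 describes as descriptive. That is correct and limits the weight of the point.

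**Conclusion.** The mismatch is real and should be corrected, but it is narrow. Three statements of the endpoint say three items. Both schedules, both tables and the listing have eight, and the SAP gives no means of telling the endpoint rows from the rest. The firm consequences are nine unadjusted p-values instead of three or four, and a tested TOTAL with no scoring rule. That five of the eight items in TOTAL fall outside the endpoint depends on two assumptions: that the phrase means three items were selected, and that TOTAL is an equally weighted sum.

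The item-level results are kept, so the three-item result can be recovered once the items are named. The primary endpoint, the sample size and the safety analysis are unaffected.

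**What to change.** 1. Reconcile the endpoint wording (protocol Secondary endpoints 4b and Acceptability assessment, SAP 2.2) with the protocol visit schedule and SAP Appendix 4, and state whether three means selected or adapted.
2. In SAP 7.2.4, identify the three items from a document that predates the data, such as the adapted questionnaire or the eCRF specification, and cite it. This matters because SAP 2.0 follows the June 2020 data review, whose minutes already speak of a second database freeze; the items must not be chosen after results are seen.
3. In Table E.4b2, make those three items the endpoint inference. If a summary is wanted, use their sum with a written scoring rule.
4. Drop the eight-item TOTAL, or label it and the other five items as additional.
5. Replace the change-from-baseline contrast with one that the Visit 4 to Visit 7 data can support, or correct the schedule if a baseline administration did take place.

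The cost is a few lines of SAP text and one table shell, with no new data. The only real work is finding the source that fixes the three items.
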